A home-based intervention to promote mindful breathing awareness through pursed-lip breathing

training for COPD patients

NCT04517500

June 8, 2021

General Study Information

Principal Investigator: [name]

Study Title: A home-based intervention to promote mindful breathing awareness through pursed-lip breathing training for COPD patients, IRB19-012772

Protocol version number and date: June 8, 2021, Version 3

Research Question and Aims

Hypothesis:

We hypothesize that providing COPD patients with a mindful breathing module that is easy-to-use, prompts them to complete daily mindful breathing practice, and provides feedback will improve their breathing mechanics, emotional awareness, increase the time that they spend in heart rate coherence, and improve their quality of life.

Aims, purpose, or objectives:

The primary outcomes of the study are changes in breathlessness and emotions. Changes from baseline to three months on the two primary outcomes will be compared between the study arms using two-sample, two-sided t-tests with 5% type I error rates. Means, SDs, medians, ranges, and frequency distributions will be reported and plotted over time by study arm. Linear models will be used to assess the impact of treatment arm on three-month outcomes after adjusting for the corresponding baseline measure and other variables related to the outcome (age, degree of breathlessness at baseline using the mMRC dyspnea, and FEV1).

Background:

COPD:

COPD is a progressive lung disease that makes breathing difficult. Breathlessness usually worsens over time and eventually may make it difficult for people to carry out regular, simple daily activities, and cause anxiety and depressive symptoms. (8,35) In the United States COPD is the fourth leading cause of death and continues to increase.(2-6) It is also the third leading cause of hospital readmission in the US. There are currently an estimated 16 million Americans diagnosed with COPD(36) and many millions more who are believed to have the disease and not know it.37,38 It is estimated that the direct costs of COPD in the United States are \$29.5 billion and the indirect costs \$20.4 billion.(39)

COPD is demanding for the individual patient due to breathlessness (dyspnea) that increases during the more severe stages of the disease and impairs quality of life.(7,40) Breathlessness is the most common symptom and the use of pharmacological treatments alone is not effective; thus, additional non-pharmacological approaches such as breath retraining exercises are suggested.(7) Anxiety and emotional symptoms are frequently associated with symptoms of breathlessness/dyspnea and the cause of higher health care utilization.(40,41)

Pulmonary Rehabilitation (PR):

PR is an intervention that combines the promotion of physical activity and self-management. (42) It is regarded as an essential component of care for people with COPD and is supported by strong scientific evidence. (43-46)

PR reduces dyspnea, shortness of breath (13, 14), increases functional exercise capacity (13, 14), improves patients' health status and sense of control over their condition (13, 14), improves health-related quality of life (14), and reduces anxiety and depression associated with COPD (14). It also reduces acute exacerbations as well as decreases hospital bed days, the number of hospital admissions (47), and the overall burden on the health system. (14, 47-59)

Breathing Practice:

Breathing practice is an important component of PR. A commonly taught technique, pursed-lipped breathing (PLB) consists of instructions to breathe through the nose like smelling a flower without forcing and exhale slowly through the mouth while pursing the lips, as if they are blowing out a candle. Patients are taught to concentrate on the breath and nothing else, like meditation. PLB can ease dyspnea (20-23,51,60) which is the most disabling symptom of COPD(7), a common reason for seeking medical attention(7), and may cause people to limit their activity.(1) PLB can prevent the large airways from collapsing and can cause the release of more air from the lungs on exhale reducing dynamic hyperinflation. (24) Current guidelines for COPD suggest that using PLB also has positive effects in treating stress and anxiety related disorders(25) and it has an acute benefit to exercise capacity and parasympathetic outflow (stress).(26) Spontaneous pursed lips breathing can be a useful technique to increase walking endurance and reduce oxygen desaturation during walking in patients with moderate to severe COPD.(27) In a study of PLB with 16 COPD patients, researchers found that while practicing PLB patients had a significant decrease in respiratory rate and a significant increase in pulse oxygen saturation.(28) These effects have been demonstrated in previous studies.(29-32) However, there has been some variability found in the effects PLB, which may be due to difficulty in tracking compliance at home and the need for ongoing guidance by a respiratory health care professional. (22) Physicians and physical, occupational, and rehabilitation therapists teach PLB to their patients to ease shortness of breath; however, the benefits are short lived and up to 50% of patients lose them due to the lack of practice.61 Research suggests that regular practice of PLB may result in long-term benefit. Patients who participated in weekly PLB training (at a lab) demonstrate improvement after 12 weeks in exertional dyspnea and physical function.(62) Mindful PLB is a critical teaching ring PR as it's a practice that improves breathing mechanics, oxygenation and emotional buoyancy during breathlessness episodes. There is no remote system to foster the home practice of mindful PLB. (40)

Cardiovascular Benefits of mindful PLB:

A guided breathing practice can have significant benefit in the cardiovascular system, the source of the most prevalent comorbidities in COPD. Briefly, the heart has a natural variation, from minute to minute, beat to beat – even sitting at rest. This phenomenon, known as Heart Rate Variability (HRV) is a sign of health, the greater the variability, the better the health. Heart rate is intimately tied to the bodily expression of emotions: in states of anxiety, fear, and sadness, extremely prevalent in patients with COPD (33, 63-66), the variation tends to be disordered and chaotic. On the contrary in positive emotional states such as gratitude, the variation tends to be rhythmic. This state of rhythmic variation is known as Heart Coherence (HRC). (67)

When the heart is in a state of coherence, HRV synchronizes with the breath – a phenomenon known as Respiratory Sinus Arrhythmia. HRC is much more than a state of relaxation. It represents a dynamic balance within the Autonomic Nervous System and its two branches, the sympathetic and the parasympathetic, which work on the heart like an accelerator and brake respectively. On the in-breath, the sympathetic branch (accelerator) is active, and heart rate increases, while on the out-breath, the parasympathetic branch (brake) is

active, and the heart slows. Healthy heart rhythms have a beneficial effect on the emotional brain. Thus, HRC facilitates positive emotion and weakens negative emotion and improves thinking: cognitive performance can be faster and more accurate. HRC is not present all the time, but a few quiet periods of coherent heart breathing at various "breaks" in the day will be restorative and balancing.

Dysfunctional breathing patterns, such as in patients with COPD, are not only biomechanically inefficient but also reflect decreased physiological resilience. (68) Slow breathing with biofeedback assists patients in spending

more time in an optimal heart rate variability pattern for health.(68-70) HRV biofeedback has been used in the treatment of multiple chronic diseases, including COPD.(68,69,71,72) The use of biofeedback, to guide the user to breathe more deeply, has reported positive effects on dyspnea in patients with COPD,(22) as well as symptoms and quality of life in heart failure and hypertension.(73) The use of biofeedback assists patients in achieving a state of mindfulness as it helps them to stay focused on the present, provides a concrete goal and motivation.

The proposed HRV biofeedback training will provide patients with information on an on-going basis allowing the patient to see the effects of effort on HRC. Using HRV biofeedback training, most individuals with COPD may learn to engage in slow, effortless PLB (24) that will put them in a state of HRC and reduce dyspnea. The proposed system is critical to creating the "habit" of mindful breathing. Once the technique is learned, and the specific practice of breathing awareness is a habit, the individual no longer needs the support of biofeedback.

Health Coaching:

A key component of the researchers' PR program is health coaching. Health coaching has demonstrated effectiveness in facilitating patient improvement in various aspects of health (74-79) by affecting patients' knowledge, skill, self-efficacy, and behavior change (74). Health coaching utilizes motivational interviewing and goal-setting to facilitate behavior change. (80,81) Health coaching is a critical component of the current Chronic Care Model that involves patient-clinician collaboration and empowers patients to take on an active role in managing their health conditions and make important health behavior changes. The conceptual foundation of health coaching is Social Cognitive (Learning) Theory.(82) Health coaching has demonstrated effectiveness in improving patient health outcomes, including health behaviors.(83) In our previous awards we demonstrated the "boosting effect" of health coaching in PR and care of COPD.(84-87) Regular feedback on a patient's health status and progress is central to the self-awareness that leads to behavior change and is also needed for proper coaching. (52) Since it is not practical or reliable (53) to collect this information daily from each patient, systems that transmit the necessary data to the health care professionals are needed. Multiple studies have found that providing regular feedback to the participant is effective in supporting behavior change. (54) Personalized feedback is more effective and preferred by patients. (54,55) In one study of COPD patients, there were clinically and statistically significant improvements in walking, QOL, selfefficacy, disability, dyspnea, and heart rate variability after using biofeedback on heart rate variability and feedback from pulse oximetry for 10 weeks.(56)

Existing PR system:

The existing PR system consists of an Android Computer tablet with Verizon service, a Nonin Pulse Oximeter and a Garmin Vivofit activity tracker. The home-based PR program is pinned on the Android tablet so that it is the home screen when the participant turns on the computer tablet and is the only accessible program on the computer tablet. The computer tablet is preloaded with a daily to-do list, daily exercises and daily questions.

The Nonin Pulse Oximeter and the Garmin Vivofit are connected to the Android tablet via blue tooth. A health coach at Mayo Clinic has access to the data through a health coach application.

Pursed Lipped Breathing Module:

Minnesota Health Solutions and Spire Health will design and integrate a PLB module and integrate it with the existing home-base PR system (currently in use in 18-002453 and 17-009449, previously used in 14-00906). The Mindful Breathing Lab ([name]) will complete a randomized control trial to evaluate the mindful breathing module. The study will evaluate the home-based PR system compared to the home-based PR system plus the mindful breathing module for its effects on breathlessness and emotions.

A mindful breathing module was created and tested for feasibility in IRB 17-004445. In this study, while wearing the Nonin Pulse Oximeter, participants inhale and exhale while following an animated ball. During an inhale, the ball climbs up a short hill, during the exhale the ball moves down a longer hill promoting pursed lipped breathing. The inhale duration is 2 seconds while the exhale duration increases from 2 to 8 seconds. The participant can tap the TOO DIFFICULT button the exhale duration will stop increasing. Please see figure 1 for an image of the mindful breathing module. In the new mindful breathing module, the breathing rate will be collected by the Spire Health Tag.

Spire Health Tags:

The Intervention system will incorporate the Spire Health Tag

Each health tag contains a battery, tri-axis accelerometer, blue tooth radio, vibro-tactile feedback mechanism, photo plethysmography sensor, and force sensor to sense relative changes in abdominal and/or thoracic excursion. The health Tags can pick up respiration, pulse rate, activity and sleep duration and quality. The Health Tags adhere to existing clothing, can withstand the washer/dryer and last for about a year without charging. The tags are attached to clothes that are worn most like bras, underwear or athletic wear. The Health tags are attached with a fabric adhesive and can be removed by peeling the unit off. The Spire Health Tags will be integrated with the existing home-based PR system. Please see Figure 2 for images of the Health Tag.

2: Respiration Sensor

As you breathe, our proprietary respiration sensor measures your thoracic excursion to assess respiratory patterns, events, and distress.

1: Ultrasuede Fabric

Health Tags are placed against your skin so it is important that they be flexible, hypoallergenic, soft, and comfortable.

3: Pulse-Rate sensor (PPG)

Spire's Photoplethysmography (PPG) Pulse-Rate sensor measures your resting HR and also helps you determine how many calories you've burned.

4: 3-axis Accelerometer

Whether you're taking a walk or working out, Spire's 3-axis Accelerometer helps youllog your steps and see how far you've gone.

Figure 2

Study Design and Methods

Methods:

This project will involve two Phases: phase one in which mindful breathing by itself without any other device will be tested to make sure that is acceptable to patients and make a difference comparing to the usual protocol in use right now. Phase two will include a particular device that will guide the mindful breathing practice that we think will be more intuitive to practice and guide the mindful breathing and that device will be tested once we know that the acceptance to the mindful breathing practice, from phase one, is appropriate.

Phase 1: A total of 70 adults diagnosed with COPD will be enrolled in the study. Half of the participants will be randomized to receive the home-based PR with the Pursed Lipped Breathing Application (intervention) and half will receive the home-based PR (control). Randomization will take place in a REDCap database and will be in equal proportion.

Phase 2: A total of 70 adults diagnosed with COPD will be enrolled in the study. Half of the participants will be randomized to receive the home-based PR with the mindful breathing module which consists of the Pursed Lipped Breathing Application and the Spire Health Tags (intervention) and half will receive the home-based PR (control). Randomization will be take place in a REDCap database and will be in equal proportion.

Both groups entail one week of baseline where the participants wear an ActiGraph activity tracker and answer questionnaires. Baseline is followed by 12 weeks of home-based PR plus health coaching. The Intervention group also has the mindful breathing module loaded on the Android tablet. Both groups will also complete questionnaires and wear an ActiGraph activity monitor at 3 and 6 months.

Please see Figure 3 for a diagram of the intervention and Figure 4 for a diagram of the control scheme.

Questionnaires:

Quality of Life will be assessed three times (baseline, 3 and 6 months) by the Medical Research Council (mMCR) questionnaire, the Chronic Respiratory Disease Questionnaire (CRQ), the Self-Management Ability Scale (SMAS30) and the Mindful Attention and Awareness Scale (MAAS). The questionnaires take about 20 minutes to complete.

At baseline additional health data will be collected from the medical record (chart review) to complete the Charlson comorbidity index, including lung function, demographics, living condition (living alone or not), GOLD stage, and comorbidities.

ActiGraph:

Physical activity will be measured three times (baseline, 3 and 6 months) by the ActiGraph activity monitor. The ActiGraph activity monitor has tri-axial accelerometers and will be wrist worn for seven days. See Figure 5. Important measures to be analyzed are daily number of steps, activity counts, minutes per day spent in daily physical activities of at least moderate intensity, and sedentary time (<2 metabolic equivalents).

Figure 5

The questionnaires and Act Graphs will be mailed to the participant with pre-paid shipping materials to send back.

Health Coaching:

All participants will receive a weekly coaching call to discuss their rehabilitation and health process. The calls are structured using motivational interviewing. The coach will review with the patient the data from the health coach system. Collaboratively, goals for rehabilitation for the following week will be set, based on information gathered and the patients' personal preferences. Each call lasts about 20 minutes. All calls will be taped to ensure compliance with the protocol.

Subject Information

Target accrual: 140

Subject population (children, adults, groups): Adults 40 years of age or older

Inclusion Criteria:

- Clinical diagnosis of COPD
- At least 10 pack years of smoking

Exclusion Criteria:

- Unable to do mild exercise (orthopedic-neurologic problems or confined to a bed)
- Unable to follow commands (cognitive impairment)
- Have a high likelihood of being lost to follow-up (active alcohol or drug abuse)
- Live in an area that does not have cellular service (Verizon)

Potential participants will have the option of meeting a study coordinator in person (if they are on campus for a clinical appointment), meeting via Video Anywhere through Epic, or meeting over the phone. If the patient desires, their consent can be digitally obtained and documented through PTRAX. The patient also has the option of receiving the consent via mail and mailing back the consent in a provided postage paid envelope. Documentation of informed consent/HIPAA authorization will involve the use of the Research Participant Tracking (PTrax) Digital Signature Capture technology for research informed consent/HIPAA authorization only while the subject, and/or the subject's representative, is in the physical presence of the person authorized to obtain consent/HIPAA authorization. The study team may print a copy of the signed consent form/HIPAA authorization form for the subject or their representative. The consent form/HIPAA authorization form will also be available to the subject via the patient portal. Note: If the subject or their representative prefers not to use the Digital Signature Capture technology, the study team will provide a paper consent form/HIPAA authorization form for signature.

Review of medical records, images, specimens

The study involves data that exist at the time of IRB submission **and** data that will be generated after IRB submission. Include this activity in the Methods section.

The study plans to conduct a retrospective chart review and ask subjects to complete a questionnaire.

Data Analysis

Sample Size

We calculated that sixty two participants will provide 80% power to detect 1 point of change in the two co primary outcomes (breathlessness and emotion as measured by the CRQ) with an alpha of 0.025. A 1 point change represents a clinically meaningful change.95 We expect about a 20 percent attrition rate (withdraw, not able to complete the 12 weeks of home-based rehab) and will therefore enroll 70 participants in each phase.

Analysis Plan

The primary outcomes of the study are changes in breathlessness and emotions. Changes from baseline to three months on the two primary outcomes will be compared between the study arms using two-sample, two-sided t-tests with 5% type I error rates. Means, SDs, medians, ranges, and frequency distributions will be reported and plotted over time by study arm. Linear models will be used to assess the impact of treatment arm on three-month outcomes after adjusting for the corresponding baseline measure and other variables related to the outcome (age, degree of breathlessness at baseline using the mMRC dyspnea, and FEV1).

The Chronic Respiratory Disease Questionnaire (CRQ) is a 20-question inventory assessing the areas of dyspnea, fatigue, emotion, and feelings of mastery. The fatigue, emotion, and mastery subscales ask patients to rate how often in the last two weeks they have been afflicted with a particular feeling or experience on a scale of 1 to 7, with higher ratings indicating less symptom impairment. The CRQ has shown to be valid and has high internal consistency reliability. Test-retest reliability is adequate in all subscales, but is particularly high in the subscales of fatigue (r=0.90), emotion (r=0.93), and mastery (r=0.91). The minimal clinically important difference for this instrument of 0.5 points is universally recognized. The Domains Dyspnea (breathlessness) and Emotions are the two co primary outcomes.

Physical activity will be measured at baseline, 3, and 6 months by the ActiGraph GX6 activity monitor, which has been used to assess physical activity in COPD populations. (92) The number of daily steps at baseline, 3,

and 6 months and across the two groups will be compared. Emotional Intelligence will be measured by the Trait Emotional Intelligence questionnaire at baseline, 3, and 6 months .(84) Mindfulness will be measured by the Mindful Attention and Awareness Scale at baseline, 3, and 6 months.(93) The participants HRC and respiratory rate will be tracked for the entire intervention period using the Spire Health Tags. At baseline additional health data will be collected from each participant's medical record to complete the Charlson comorbidity index, including lung function, demographics, living condition (living alone or not), GOLD stage, and comorbidities.

References:

1. National Heart Lung and Blood Institute. Diseases and Conditions Index, COPD. Retrieved on March 23, 2009 http://www.nhlbi.nih.gov/health/dci/Diseases/Copd/Copd_WhatIs.html.

5. Petty TL. Scope of the COPD problem in North America: early studies of prevalence and NHANES III data: basis for early identification and intervention. Chest 2000;117(5 Suppl 2):326S-331S.

6. Heron M. Deaths: Leading causes for 2016. National Vital Statistics Report. 67(6):1-76. July 26, 2018.

8. Xu W et al. Independent effect of depression and anxiety on chronic obstructive pulmonary disease exacerbations and hospitalizations. Am J Respir Crit Care Med. 2008 Nov 1;178(9):913-20. doi: 10.1164/rccm.200804-6190C.

9. Guell R et al. Long-term effects of outpatient rehabilitation of COPD: A randomized trial. Chest 2000;117(4):976-83.

10. From the Global Strategy for the Diagnosis, Management and Prevention of COPD, Global Initiative for Chronic Obstructive Lung Disease (GOLD) 2014. Available from: http://www.goldcopd.org/.

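### Rehab non-completion is counted as attrition and the primary test is an unadjusted t-test on available 3-month CRQ scores; a baseline-adjusted repeated-measures model on all randomised participants would be safer and more precise

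*Combined protocol and SAP*

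**What the plan says.** All references are to the combined protocol and SAP.

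- **Data Analysis, Sample Size.** The plan states "We calculated that sixty two participants will provide 80% power to detect 1 point of change" on the two CRQ domains, "with an alpha of 0.025". It then allows for loss: "We expect about a 20 percent attrition rate (withdraw, not able to complete the 12 weeks of home-based rehab". Enrolment is set at 70 per phase.
- **Data Analysis, Analysis Plan.** The primary comparison is: "Changes from baseline to three months on the two primary outcomes will be compared between the study arms using two-sample, two-sided t-tests", at a 5% type I error rate. Linear models for the 3-month outcome, adjusted for baseline CRQ, age, mMRC and FEV1, are listed as a further analysis. Descriptive summaries by arm over time are also planned. The CRQ minimal important difference is given as 0.5 points.
- **Study Design and Methods.** "Both groups will also complete questionnaires and wear an ActiGraph activity monitor at 3 and 6 months". The CRQ is scheduled at baseline, 3 and 6 months. Questionnaires go out by post with prepaid return materials.

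The document has no intention-to-treat statement, no analysis population, no method for a missing 3-month CRQ and no sensitivity analysis. It does not say whether follow-up continues after someone stops rehab.

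**The concern.** The attrition sentence merges two different things: a missing outcome, and failure to finish the treatment programme. Only the first has to remove someone from the analysis. The outcome is a mailed questionnaire, so a person who stops rehab in week 5 can still supply a 3-month score.

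Non-completion follows randomisation and could differ by arm, because only the intervention arm has the added breathing module and its daily practice. If the study team reads the attrition sentence as permission to stop mailing to non-finishers, or to leave them out, the groups compared are no longer the groups randomised. Nothing in the plan rules this out.

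The stated primary test also handles incomplete data poorly. It makes no use of the baseline score beyond subtraction. A participant who misses month 3 but returns the 6-month form contributes nothing to it.

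**Working it through.** **1. The plan's own figures.** No SD of change is given, so it has to be back-solved. Inputs: 62 participants at 1:1 (31 per arm), a 1-point difference, 80% power, alpha 0.025 taken as two-sided. Solving the noncentral t power equation with SE = SD × √(2/31) gives SD ≈ 1.25 (1.28 by the normal approximation). If the 0.025 is one-sided, SD is 1.38 to 1.41. I use 1.25 as an assumption.

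The planned 20% loss from 70 leaves 70 × 0.80 = 56, or 28 per arm, and 14 lost per phase. The document does not split these 14 between withdrawals and rehab non-finishers. (Separately, 62/0.80 = 77.5, so 70 does not deliver 62 after 20% loss. That is a different point, but it is why 28 per arm is used here.)

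**2. Bias if non-finishers are left out.** Let d_I and d_C be the non-completion proportions in the intervention and control arms, and let non-finishers' mean change be g points worse than finishers' in both arms. Then

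bias = completer difference − all-randomised difference = g × (d_I − d_C).

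None of these inputs is in the document; all are assumed.

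| d_I v d_C | g | Bias (points) |
|---|---|---|
| 20% v 20% | any | 0 |
| 25% v 15% | 0.5 | 0.5 × 0.10 = 0.05 |
| 25% v 15% | 1.0 | 1.0 × 0.10 = 0.10 |
| 30% v 10% | 0.5 | 0.5 × 0.20 = 0.10 |
| 30% v 10% | 1.0 | 1.0 × 0.20 = 0.20 |
| 15% v 25% | 0.5 to 1.0 | −0.05 to −0.10 |

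Equal 20% loss does not guarantee zero bias. If the finisher/non-finisher gap is 0.5 to 1.0 point larger in the intervention arm, the bias is 0.20 × 0.5 to 0.20 × 1.0 = 0.10 to 0.20.

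**3. Effect on the type I error at the planned two-sided 5%.**
- 30% v 10%, g = 1: about 24 v 32 completers. SE = 1.25 × √(1/24 + 1/32) = 0.338, noncentrality 0.20/0.338 = 0.59, rejection about 9% (about 8% if SD is 1.38).
- 25% v 15%, g = 0.5: bias 0.05, noncentrality about 0.15, rejection about 5.2%.

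**4. Precision.** Assume equal CRQ variance at each visit, a baseline to follow-up correlation r of 0.5 to 0.7, and a 3-to-6-month correlation 0.1 higher.
- *Planned change t-test:* SE = 1.25 × √(2/28) = 0.334.
- *Baseline adjustment alone:* the residual variance is 1.25² × (1 + r)/2. At r = 0.5, SE = √(1.172 × 2/28) = 0.289; at r = 0.7, SE = √(1.328 × 2/28) = 0.308. Reduction: 1 − 0.289/0.334 = 13% to 1 − 0.308/0.334 = 8%.
- *Repeated-measures model at 0, 3 and 6 months, baseline means constrained equal:* generalised least squares with 35 per arm, of whom 28 have all visits, 3.5 have baseline and 6 months only, and 3.5 have baseline only. SE is 0.286 (r = 0.5) to 0.302 (r = 0.7), which is 14% to 10% below the t-test.
- *Contribution of the 6-month data:* 0.286 against 0.289 and 0.302 against 0.308, about 1-2%.

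**5. Power when non-finishers are kept** (SD 1.25, two-sided alpha 0.025, t-test). With 56 completers and a 1-point effect, power is about 75%. With all 70 observed at 3 months it is 85% if non-finishers get the full effect, 76% if they get half (mean effect 0.8 + 0.2 × 0.5 = 0.9), and 65% if they get none (mean effect 0.8). Keeping everyone protects the comparison but does not always raise power.

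**The case against.** A reader might infer that the plan prescribes a completer analysis and that 14 of 70 people per phase will be dropped for not finishing rehab. The documents do not support that. The attrition phrase is a sample-size assumption and not an exclusion rule. The Analysis Plan compares the study arms without restricting to completers, and the Methods have both groups complete questionnaires at 3 and 6 months with no condition on finishing. A non-finisher who returns the 3-month CRQ is in the t-test as written. The 14 also pools withdrawals with non-finishers, so the number at risk of exclusion for non-completion is unknown.

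The other objections stand in part:
- The 0.20-point bias and 9% rejection rate come from an unfavourable assumed scenario. Both arms get the same 12-week rehab and weekly coaching, and the module's prompts could help retention, so the bias could be nil or reversed.
- It would be wrong to say that the 6-month CRQ is ignored or that using it brings a large gain. Summaries over time are planned, and its effect on the SE is only about 1-2%.
- Baseline adjustment is already in the plan, but only as a further model. The stated primary test remains the unadjusted one.
- A likelihood-based model assumes data are missing at random. It does not by itself remove bias from outcomes that are missing because they are poor. Hence the need to follow non-finishers and to add a sensitivity analysis.

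**Conclusion.** The concern holds in a limited form. The plan conflates stopping rehab with losing the outcome, and its primary analysis is an unadjusted available-case t-test. Whether that turns into a completer comparison depends on conduct that the document leaves open. If it does, the bias under the assumed inputs lies between 0 and 0.20 points in the intervention's favour, at most 0.20/0.5 = 40% of the plan's minimal important difference, and could run the other way if control loses more people.

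The firmer gain is in precision: an SE 10-14% lower than that of the stated primary test, nearly all from baseline adjustment. This rests on the back-solved SD of 1.25, 28 per arm and correlations of 0.5-0.7. The main role of the 6-month CRQ is to keep people who miss month 3 in the model under missing at random. Missing intention-to-treat and missing-data wording would alone be a request for clarification; a better primary method at little cost makes a change worthwhile.

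**What to change.** 1. Make the primary analysis, for each of the two CRQ domains, a baseline-adjusted, likelihood-based repeated-measures model on baseline, 3 and 6 months (arm by time, with baseline constrained equal or as a covariate, plus the covariates already listed). The 3-month contrast is primary. Include every randomised participant by assigned arm, whether or not they finish rehab.
2. In the Sample Size section, separate rehab non-completion from a missing outcome. State in the Methods that the 3- and 6-month questionnaires are mailed to people who stop rehab, unless they withdraw from follow-up.
3. Keep the t-test on change as a supportive analysis.
4. Add one sensitivity analysis that assumes worse outcomes for missing values.

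Cost: revised plan wording, a slightly more complex model that needs a stated covariance structure, and a few prepaid mailings. No new data items are needed. If non-finishers benefit less, the estimated effect will be smaller than among finishers; that is the effect of assignment, and the power statement should reflect it.

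### The sample-size paragraph's 62 participants, about 20% attrition and 70 per phase do not fit together: 20% loss from 70 leaves 56, and 70 protects 62 only up to about 11% loss

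*Combined protocol and SAP*

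**What the plan says.** Under Data Analysis, Sample Size, the plan states that "sixty two participants will provide 80% power to detect 1 point of change in the two co primary outcomes", at an alpha of 0.025 whose sidedness is not given. The next step expects a "20 percent attrition rate (withdraw, not able to complete the 12 weeks of home-based rehab) and will therefore enroll 70 participants in each phase", so 70 is presented as the result of inflating 62 for attrition.

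The enrolment figure is consistent elsewhere. Study Design and Methods has "Phase 1: A total of 70 adults diagnosed with COPD will be enrolled in the study" and "Phase 2: A total of 70 adults diagnosed with COPD will be enrolled in the study", each randomized equally between two arms, and Subject Information has "Target accrual: 140". So 70 is the total per phase, 35 per arm.

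The Analysis Plan says that three-month changes in the two co-primary CRQ domains will be "compared between the study arms using two-sample, two-sided t-tests with 5% type I error rates". No SD for the change in either domain is given anywhere.

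**The concern.** The paragraph presents 70 as derived from 62 and 20%, but neither the correct inflation nor the usual shortcut gives 70. At the attrition the plan itself expects, the evaluable number falls below the number on which the power claim rests.

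At stake is the one power statement in the document, which is the sole stated justification for enrolling 70 people in each phase (140 in all). If 14 participants per phase are lost as expected, the claimed 80% is not what the design delivers at the alpha used for sizing.

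**Working it through.** **Inputs.** All are from the Sample Size paragraph unless noted.
- Required number: 62, with equal arms (Study Design and Methods), so 31 per arm
- Power 80%, difference 1 point, alpha 0.025 (sidedness not stated)
- Attrition: about 20%
- Enrolment: 70 per phase (also in Study Design and Methods)
- Test level in the Analysis Plan: two-sided 5%

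**Attempt to reproduce 70.**
- Correct inflation, N/(1 − d): 62/0.80 = 77.5, so 78
- Common shortcut, N × (1 + d): 62 × 1.20 = 74.4, so 75
- Neither gives 70.

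**Working back from 70.**
- Completers: 70 × 0.80 = 56, and 62 − 56 = 6 short
- Losses expected: 70 × 0.20 = 14. Losses that 70 can absorb: 70 − 62 = 8
- Largest loss that keeps 62: 1 − 62/70 = 11.4%

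**Other readings.**
- 'About 20%' read loosely as 15%: 70 × 0.85 = 59.5, still below 62
- 62 per arm: 124/0.80 = 155 per phase, further from 70

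**Effect on power.** With no SD stated, I take the plan's claim that 62 gives 80% as true and back-solve the standardized difference, using the noncentral t for two equal arms. Power is per outcome, for 1 point.

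| Alpha used to size 62 | Alpha used to test | Implied d (SD for 1 point) | 62 evaluable | 56 evaluable |
|---|---|---|---|---|
| two-sided 0.025 | two-sided 0.025 | 0.800 (1.25) | 80% | 75.2% |
| one-sided 0.025 | two-sided 0.05 | 0.723 (1.38) | 80% | 75.7% |
| two-sided 0.025 | two-sided 0.05 | 0.800 (1.25) | 87.3% | 83.6% |

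In the first two rows, the difference detectable with 80% power rises from 1.00 to about 1.05 points: 0.844/0.800 and 0.762/0.723, where 0.844 and 0.762 are the standardized differences giving 80% power with 28 per arm. If 62 was rounded up from a total as low as 60, the 56-evaluable figures in those rows are at most 76.8% and 77.1%. The implied SDs only show the range and are not proposed for the protocol.

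**The case against.** The strongest reply has three parts.

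First, the plan's attrition includes people who do not complete the 12 weeks of rehabilitation, and that is not the same as a missing primary outcome. The three-month questionnaire is mailed with prepaid return, so a non-completer could still send it back. If 6 of the 14 expected losses did so, 62 would be analysable. This is possible, and it means 56 is a planning number rather than a forecast. But the document does not split the 20% or say that non-completers will be analysed, and it uses the whole 20% as its reason for enrolling 70.

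Second, an alpha of 0.025 stated beside two co-primary outcomes can naturally be read as 5% split in two. If so, and if each outcome is then tested at two-sided 5% as the Analysis Plan says, power with 56 is 83.6%. Even 52 evaluable (26 per arm) would give 80.7%. This stands as a calculation. It depends, however, on the sizing alpha differing from the testing alpha, which is a separate inconsistency between the Sample Size and Analysis Plan paragraphs. If that is resolved by testing at two-sided 0.025, the margin disappears. In neither case does 70 follow from 62 and 20%.

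Third, the effect is small: 4 to 5 percentage points of power at matched alpha. That is fair and limits the weight of the point, but it does not make the derivation right.

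**Conclusion.** The concern holds. As stated, 62, about 20% and 70 are not mutually consistent, and nothing else in the document reconciles them. That conclusion is pure arithmetic and needs no assumption. The shortfall is 6 evaluable participants per phase, or equivalently an attrition allowance of 11.4% where the plan expects about 20%.

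The effect on power is conditional. It rests on the plan's unverified claim that 62 gives 80%, on 56 evaluable with 28 per arm, and on power considered one outcome at a time. Under those assumptions it is about 75–76% when sizing and testing alphas match, and 83.6% when 62 was sized at two-sided 0.025 but tested at two-sided 5%. It should be fixed, but the effect is modest.

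**What to change.** Keep 70 per phase and correct the Sample Size paragraph in one of two ways.

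(a) State that about 20% attrition leaves 56 evaluable per phase. Give the SD used, and report power recomputed from it at the alpha actually applied to the two co-primary tests. If that alpha is two-sided 0.025 and 62 was sized at that level, expect about 75%.

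(b) State that 70 preserves 62, and so the claimed 80%, only up to about 11% loss. Replace the 20% figure if a lower rate can be justified. The document gives no basis for one at present.

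Under either option, a sentence saying whether participants who stop rehabilitation but return the three-month questionnaire count as evaluable would settle what the 20% means.

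The cost is a wording change in one paragraph, with enrolment, endpoints and tests unchanged. The downside is a less favourable stated power under (a), or a tighter attrition limit to defend under (b). Preserving 62 at 20% loss by enrolment instead would take 78 per phase, 156 rather than 140 overall. That is a larger change than the error requires.
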